2.10 Analysis plan

Baseline data will be summarized descriptively. The primary outcome of 90-day mortality will be evaluated using an intent-to-treat approach. A simple comparison of proportions will be performed using a chi-squared test. The risk ratio and relative risk reduction will be estimated with 95% confidence intervals. An adjusted analysis will also be completed using logistic regression and will include the following baseline variables: age, sex, sepsis, receipt of cardiopulmonary bypass and SOFA score.

The principal secondary outcome, the proportion of survivors who are RRT dependent at 90 days, presents challenges as the non-inclusion of participants who died might obviate the inter-group balance afforded by randomization. We will consider two complementary approaches to examine this question. First, we will use the adjusted model for the primary outcome to estimate the probabilities of 90-day survival. We will then use the reciprocals of these as weights in a logistic regression for RRT, resulting in an inverse probability weighted analysis. This is typically called a marginal structural model. The second approach will employ a multinomial regression model to jointly consider the states: dead at 90 days, alive at 90 days receiving RRT and alive at 90 days RRT-free. A similar approach will be used to estimate the probabilities of 365-day survival and to consider the states: dead at 365 days, alive at 365 days receiving RRT and alive at 365 days RRT-free.

Duration of ventilation, vasoactive therapy, ICU stay and hospitalization and albuminuria at 90 days (expressed as the urinary albumin to creatinine ratio in mg/mmol) will be compared by means of a t-test. Finally, eGFR decline of 25%, death in ICU, by 28 days and in-hospital, and ICU readmission and rehospitalization within 90 days will be compared by chi-squared tests.

Interim analyses for efficacy based on the primary outcome will be done when 25, 50 and 75% of planned enrollees have completed 90-day follow-up. Given the risks of false positive results with early stopping for benefit, statistical significance will be declared using small p-values established by O'Brien-Fleming boundaries on the primary outcome (90-day mortality). A detailed monitoring plan will be developed in consultation with the DSMB prior to commencement of recruitment.

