the ICU and/or nephrology attending physician and ask if they agree with the statement: "RRT must be initiated immediately in this patient" If the answer is "Yes", the patient will be excluded but may be rescreened for eligibility; and ● the clinicians caring for the patient believe that deferral of RRT is mandated. After fulfilling the above inclusion/ exclusion criteria, the study team will speak to the ICU and/or nephrology attending physician and ask if they agree with the statement: "RRT must be deferred in this patient" If the answer is "Yes", the patient will be excluded but may be rescreened for eligibility.

Randomisation, treatment allocation and blinding

Intervention

Patients enrolled in the STARRT-AKI trial will be randomly allocated to receive either accelerated (early) initiation of RRT, defined as start of RRT within 1 2 hours of fulfilling eligibility, or standard (delayed) initiation of RRT, whereby

RRT initiation is discouraged unless one or more clinical criteria for RRT develop and/or the attending physician determines that deferral of RRT is no longer in the patient's best interest. Eligible patients will be allocated 1 :1 by randomised permuted blocks (of variable size) and stratified by site, using a dedicated web-based platform.

Primary outcome

The primary outcome is all-cause mortality 90 days after randomisation.

[figure not shown]
Secondary outcomes

The secondary outcomes are:

- RRT dependence at 90 days after randomisation among surviving patients;
- composite of death and/or RRT dependence at 90 days after randomisation; ● composite of major adverse kidney events, defined as death, RRT dependence or sustained reduction in kidney function (defined as eGFR < 75% baseline eGFR) at 90 days after randomisation, 1 1 ● eGFR among surviving patients at 90 days after randomisation; ● albuminuria among surviving patients at 90 days after randomisation; ● death in the ICU, at 28 days after randomisation, and inhospital;
- RRT-free days to 90 days after randomisation; ● ventilator-free days and vasoactive therapy-free days to 28 days after randomisation; ● length of ICU stay and ICU-free days to 28 days after randomisation, ● length of hospitalisation and hospitalisation-free days to 90 days after randomisation; and ● health-related quality of life, using the EuroQoL EQ5D-5L scale, among surviving patients at 90 days after randomisation. 1 2

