The number and percentage of deaths through 90 days after randomisation will be reported for each treatment group. The primary effect estimate will be the relative risk of 90-day mortality, reported with 95% CI. The absolute risk difference and 95% CI will also be reported. Deaths up to 90 days after randomisation will be compared between the treatment groups using test. Additionally, the odds ratio (OR) (95% CI) will also be determined, primarily to permit comparisons between the primary unadjusted analysis and the various secondary pre-specified adjusted analyses of 90day mortality (Table 2).

Adjusted sensitivity analysis

Death at 90 days will also be analysed, adjusting for baseline characteristics (eg, age, sex, baseline eGFR, Simplified Acute Physiology Score [SAPS] II score at randomisation, surgical status, and presence of sepsis). Continuous variables (eg, age, eGFR and SAPS II score) will be modelled using restricted cubic splines with four knots to accommodate the possibility of non-linear relationships with the log odds of death. The OR and 95% CI will be determined first, primarily to permit comparisons between the unadjusted analysis and the secondary adjusted analyses of 90-day mortality. The adjusted treatment effect will be reported as the adjusted OR (95% CD. Should the adjusted OR be materially different from the unadjusted OR, a second adjusted model will be fit that employs the log link to provide adjusted estimates of the risk ratio. An additional sensitivity analysis will include site as a random effect in a generalised linear mixed model to assess if the variance component is important and affects inference.

Treatment of missing data

If more than 5% of patients from the ITT population are excluded from the adjusted analysis of the primary outcome due to missing data for baseline covariates, missing data will be imputed using fully conditional specification ²⁰ The imputation model will include all covariates required for the adjusted analysis as well as other baseline variables deemed related to the variables for which imputations are required. The multiple imputation will then be performed via chained equations to obtain ten imputed datasets. The adjusted analysis will be performed on the imputed datasets with the results appropriately pooled.

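### The primary 90-day mortality test is valid and adequately powered, but leaves out prognostic baseline variables that the SAP already models only as a sensitivity analysis; adjusting would be a cheap gain in precision

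*SAP*

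**What the plan says.** Protocol section 2.10 sets the primary test: "A simple comparison of proportions will be performed using a chi-squared test". An adjusted logistic regression is added to it, with "age, sex, sepsis, receipt of cardiopulmonary bypass and SOFA score" as covariates.

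The SAP keeps that order. Under Principal analysis, "Deaths up to 90 days after randomisation will be compared between the treatment groups", and the primary estimate is the relative risk. The same paragraph separates "the primary unadjusted analysis and the various secondary pre-specified adjusted analyses". Under Adjusted sensitivity analysis, "Death at 90 days will also be analysed, adjusting for baseline characteristics", with the covariates given as "eg, age, sex, baseline eGFR, Simplified Acute Physiology Score [SAPS] II score at randomisation, surgical status, and presence of sepsis". Age, eGFR and SAPS II enter as restricted cubic splines, and the result is an adjusted odds ratio. A log-link model for the risk ratio follows only if the two odds ratios differ materially. Missing covariates are imputed only if more than 5% of patients would otherwise drop out of the adjusted analysis.

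Randomisation is 1:1 "and stratified by site, using a dedicated web-based platform", with no severity stratum. The SAP's Analysis principles set a final level of 0.044 after three O'Brien-Fleming interim looks. Neither document gives a reason for leaving the primary test unadjusted.

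**The concern.** The plan itself treats these variables as prognostic. It allows for non-linear relations between them and death, its Table 1 footnote ties higher SAPS II scores to a higher risk of death, and it uses SAPS II as predicted baseline risk when looking for treatment-effect heterogeneity. In an ICU population of mixed severity, such variables explain part of the variation in death. A test that ignores them has a larger standard error than the same patients could give. Because only site is stratified, balance in severity is left to chance, and the deciding comparison does not correct for it. At stake are some power and a narrower interval, from data and a model that already exist.

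**Working it through.** **Inputs.** Protocol 2.9: mortality 40% against 34%, two-proportion design, power 0.90, 1,359 per arm (2,718), 2,780 after allowing for interim looks, 2,866 after 3% crossover and dropout. SAP: two-sided tests, interim thresholds 0.00001473, 0.003045 and 0.0183, final level 0.044 (z = 2.014), recruitment extended to at least 3,000.

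**1. The plan's own figures.** The two-proportion formula with pooled variance, two-sided alpha 0.05 and no continuity correction gives 1,359 per arm, 2,718 in total: an exact match. 2,780/0.97 = 2,866: also exact. The step from 2,718 to 2,780 is taken as stated. The sample size therefore rests on the unadjusted test.

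**2. Power of the unadjusted test.** The expected z is 0.06/sqrt(2 × (0.40×0.60 + 0.34×0.66)/N).
- N = 2,866: 0.06/sqrt(0.9288/2,866) = 3.333; power = Φ(3.333 − 2.014) = 90.6%.
- N = 3,000: 3.410; power = Φ(1.396) = 91.9%.

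These are fixed-sample figures, before the 3% loss and the small cost of the interim looks.

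**3. Gain from adjustment.** If baseline covariates explain a share R² of the variance in death, the expected z becomes 3.333/sqrt(1 − R²), and the gain equals 2,866 × R²/(1 − R²) extra patients. The documents give no R² or c-statistic, so R² is assumed. The c values come from a logistic-normal risk model at pooled mortality 0.37.

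| Assumed R² | c, about | Equivalent extra patients | Power at 2,866, level 0.044 |
|---|---|---|---|
| 3.0% | 0.60 | 89 | 91.5% |
| 5.6% | 0.64 | 170 | 92.2% |
| 10.5% | 0.69 | 336 | 93.4% |
| 16.8% | 0.74 | 579 | 95.0% |

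The result depends strongly on the assumption: c = 0.55 gives about 21 patients and c = 0.80 about 1,008. Simulated trials of 2,866 patients (1,500 runs each) gave efficiency ratios for adjusted logistic regression against chi-squared of 1.07 at c about 0.64 and 1.17 at c about 0.73. These are worth about 191 and 481 patients, in line with the formula.

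**4. Chance imbalance.** The standard error of the risk difference is 0.06/3.333 = 1.80 percentage points. The covariate-driven part has a standard deviation of sqrt(R²) × 1.80: 0.31 points at R² = 3% and 0.74 points at 16.8%, against a target effect of 6 points.

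**5. Overall alpha if only the last look is adjusted.** The documents do not state the interim statistic; I assume that it was unadjusted. Under the null hypothesis, the correlation of the final z with the z at information fraction t is then sqrt(t) × sqrt(1 − R²), not sqrt(t). With looks at 25%, 50%, 75% and 100% and the SAP's four thresholds:

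| R² | Overall alpha at final level 0.044 | Final level that holds 5% | Power at 2,866 at that level |
|---|---|---|---|
| 0 | 0.0500 | 0.0440 | 90.6% |
| 3.0% | 0.0505 | 0.0434 | 91.4% |
| 5.6% | 0.0509 | 0.0429 | 92.0% |
| 10.5% | 0.0517 | 0.0420 | 93.2% |
| 16.8% | 0.0527 | 0.0410 | 94.6% |

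The first row confirms the SAP's boundary. Most of the gain survives the correction.

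**6. Missing covariates.** If the 5% rule carried over to the deciding test, up to 5% of patients could drop out of it. The effective size is 0.95 × 2,866/(1 − R²): 2,807 at R² = 3% (a loss of 59), 2,884 at 5.6% (a gain of only 18) and 3,042 at 10.5% (a gain of 176).

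**The case against.** The case for leaving the plan alone is substantial. Design and analysis agree, the test is valid, and power already meets the 90% target, more so after the extension to 3,000. Type I error already allows for chance imbalance, and with 2,866 patients the imbalance is small. The SAP also prints adjusted and unadjusted odds ratios together, so a severity imbalance would show. The change would come late: the SAP is dated 23 May 2019, after the third interim analysis of 24 April 2019, and it reports no protocol amendment since October 2015. A new statistic at the last look alone disturbs the boundary. The unadjusted test needs no covariates and loses no patient to missing ones. All of this stands. It makes the point an improvement and shapes the fix; it does not remove the gain.

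Three stronger readings are tempting, and the documents support none of them. A reader might infer that the trial gives up a known number of patients, but any such figure rests on an assumed prognostic strength found in neither document. A reader might infer that the trial is underpowered or its test wrong; step 2 shows otherwise. And a reader who finds "Deaths up to 90 days after randomisation will be compared between the treatment groups using test" without a test name should not conclude that none was chosen: a symbol appears to have been lost in text conversion, and the protocol names chi-squared.

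**Conclusion.** The point holds as lost efficiency. The deciding test omits prognostic variables that are collected and modelled elsewhere in the same SAP, and no reason is given. If those variables explain 3% to 17% of the variance in death, adjustment is worth about 90 to 580 patients at 2,866. Power then rises from 90.6% to about 91.5% to 95%, or about 91.4% to 94.6% once the final level is corrected. The size rests on the assumed R², on the plan's 40% and 34%, and, for the corrected level, on unadjusted interim looks at 25%, 50% and 75% of information. The change is worth making because it costs little, not because the planned result would be unreliable.

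**What to change.** Before database lock, and decided by people without access to interim results:

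1. Make the primary estimate and test the standardised (marginal) relative risk and risk difference from a logistic model, with a delta-method or bootstrap interval. This keeps the planned relative-risk target, which a conditional odds ratio does not.
2. Fix the covariate list: age, sex, SAPS II, sepsis and surgical status, with region optional. The SAP's list is only illustrative and differs from the protocol's, which has SOFA and cardiopulmonary bypass. State why baseline eGFR is left out, or how its missing values are handled.
3. Keep every intention-to-treat patient in this test by imputing missing baseline covariates at any level of missingness, not only above 5%.
4. Recompute the final significance level for the change of statistic, at the actual information fractions, so that overall alpha stays at 5%. Expect about 0.043 to 0.041 if the interim looks were unadjusted.
5. Keep the unadjusted chi-squared result as a supporting analysis.

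The cost is SAP text, a modest amount of programming, a slightly smaller final alpha, and a late departure from the protocol's test that must be documented and explained. If the sponsor prefers to keep chi-squared as primary, the least it should do is give the reason and pre-specify the standardised adjusted relative risk, with a fixed covariate list, beside it.

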- The secondary analyses will not be adjusted for multiple testing; however, the results of all statistical testing will be reported according to the American Statistical Association guidelines to provide the necessary context for interpretation.¹⁷
- All estimates of treatment effect will be accompanied by 95% confidence intervals (CI).
- All analyses will be performed using the R software package (R Core Team, 2008; www.R-project.org).

Interim analyses and the Data Safety Monitoring Board

An independent DSMB will review unblinded data to examine recruitment rate, patient characteristics, randomisation compliance, treatment compliance, completeness of data, outcomes and adverse events on three occasions (following the completion of 90-day follow-up for the 716th, 1432nd and 2150th patient, respectively). The DSMB charter is available at: <https://www.ualberta.ca/critical-care/research/current-research/starrtaki/documents.10>

Analysed datasets

All main analyses will be performed on the ITT population dataset. For these analyses, all patients will be analysed according to the group to which they were randomised; however, any randomised patient found to have not fulfilled eligibility criteria based on data available at the time of initial assessment (ie, randomised in

error) will be excluded following independent adjudication by two investigators who will be blinded to outcomes.¹⁸

Trial profile

The flow of patients through the trial will be shown in a Consolidated Standards of Reporting Trials (CONSORT) diagram (Figure 1).¹⁹ The figure will provide a summary of the number of patients screened, the number of patients who fulfilled eligibility, the number of patients who were excluded and the reason(s) for exclusion.

Patient characteristics and baseline comparisons

- A description of baseline characteristics will be presented by treatment allocation, as outlined in the proposed Table 1 .
- Categorical variables will be summarised with frequencies and percentages. Percentages will be calculated according to the number of patients for whom data are available.

- Continuous variables will be summarised as means with standard deviation (SD) or medians with the interquartile range (IQR) (Q1 and Q3).

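### The SAP gives an adjusted risk ratio for 90-day death only after an undefined comparison of odds ratios; standardising the planned logistic model would give it every time at little cost

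*SAP*

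**What the plan says.** Under Principal analysis the SAP sets the scale: "The primary effect estimate will be the relative risk of 90-day mortality, reported with 95% CI". It adds: "The absolute risk difference and 95% CI will also be reported". An unadjusted odds ratio is also computed, mainly so that it can be compared with adjusted results.

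Under Adjusted sensitivity analysis the model is logistic, "adjusting for baseline characteristics (eg, age, sex, baseline eGFR, Simplified Acute Physiology Score [SAPS] II score at randomisation, surgical status, and presence of sepsis", and the continuous covariates "will be modelled using restricted cubic splines with four knots". The result is on the odds scale: "The adjusted treatment effect will be reported as the adjusted OR". A risk ratio comes only through the conditional sentence: "Should the adjusted OR be materially different from the unadjusted OR, a second adjusted model will be fit that employs the log link". The SAP does not say how large a difference is material, which distribution goes with the log link, or what happens if that model does not converge. Under Analysis principles it says: "All analyses will be performed using the R software package".

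Protocol 2.10 plans a risk ratio for the primary comparison and an adjusted logistic regression on a closed covariate list: "age, sex, sepsis, receipt of cardiopulmonary bypass and SOFA score". Neither document gives another route to an adjusted risk ratio or any adjusted risk difference. The SAP refers to an online appendix, which was not available for this review.

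**The concern.** A reader of the primary relative risk and risk difference will want the covariate-adjusted values on the same scales. The risk difference is never adjusted, and whether the risk ratio is adjusted depends on a judgement made with the results in hand. The next section of the SAP, on missing data, sets a numerical trigger for imputation (more than 5% of patients excluded), so the missing threshold here is conspicuous.

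The comparison is also a poor signal. Odds ratios are non-collapsible: if treatment has an effect and the covariates predict death, the adjusted odds ratio lies further from 1 than the unadjusted one even when the arms are perfectly balanced. The trigger therefore responds partly to the size of the treatment effect and the strength of the covariates. It can fire when adjustment leaves the risk ratio alone, and stay silent when the risk ratio does shift.

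**Working it through.** **Inputs from the documents.** 90-day mortality of 40% against 34% (relative reduction 15%, absolute 6%), two-sided 5% alpha, 90% power, 1:1 allocation (Protocol 2.9 and 2.3.1; SAP, Sample size). The simulations of the trigger use N = 3,000, the extended minimum in the SAP.

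**Assumption.** The documents give no prognostic strength for the covariates. I take their combined contribution to the log-odds of death as normal with SD 0.5, 0.75 or 1.0.

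**The plan's own figure.** With pooled variance,

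n per arm = [1.960·√(2·0.37·0.63) + 1.282·√(0.40·0.60 + 0.34·0.66)]² / 0.06² = (1.338 + 0.873)² / 0.0036 ≈ 1,359,

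as stated. The final inflation is 2,780 / 0.97 = 2,866, also as stated. No stated number is in dispute.

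**Step 1: the gap under perfect balance.** The unadjusted odds ratio is (0.34/0.66) / (0.40/0.60) = 0.773. For each SD s, solve for the intercept a and treatment coefficient b so that the average of expit(a + sZ) is 0.40 and the average of expit(a + b + sZ) is 0.34, with Z standard normal. The adjusted odds ratio is exp(b).

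| SD | Adjusted OR | Ratio to 0.773 | Risk ratio |
|---|---|---|---|
| 0.5 | 0.762 | 1.4% lower | 0.85 |
| 0.75 | 0.749 | 3.0% lower | 0.85 |
| 1.0 | 0.734 | 5.0% lower | 0.85 |

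None of this gap reflects imbalance.

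**Step 2: how often the trigger fires.** Trials were simulated from the same model. In each, the adjusted and unadjusted odds ratios were compared, and so were the standardised and unadjusted risk ratios. The cut-offs are mine, because the SAP has none.

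| | SD 0.5 | SD 0.75 | SD 1.0 |
|---|---|---|---|
| OR gap above 5%, true RR 0.85 | about 2% | about 21% | about 50% |
| OR gap above 10%, true RR 0.85 | 0% | 0.3% | about 6% |
| OR gap above 5%, no effect | about 1% | about 6% | about 14% |
| RR moved by more than 5%, true RR 0.85 | 0% | 0.2% | 1.1% |

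At RR 0.85, about 15%, 56% and 70% of the firings at the 5% cut-off came when adjustment moved the risk ratio by less than 2%. With no effect the shares were 0%, 3% and 9%. Conversely, when the risk ratio did move by 2% or more (RR 0.85), the 5% trigger stayed silent in 50% to 73% of trials.

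**Step 3: the follow-on model.** The answer depends on the distribution, which the SAP leaves open.

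- Binomial with log link, in R with an admissible start: no converged interior fit in 41% to 47% of trials at SD 0.5 and in 99% to 100% at 0.75 and 1.0, but in none at SD 0.3. A separate implementation at N = 2,866 reached an interior solution in 99% of trials at SD 0.3, 68% at 0.5, 4.5% at 0.8 and 0.5% at 1.0. The exact rate depends on the set-up; the pattern does not.
- Poisson with log link: a stable risk ratio throughout (median 0.849 to 0.852 for SD 0.8 to 1.5, true 0.85), although some trials have fitted risks above 1.

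**Step 4: the alternative.** Standardising the adjusted logistic model gave a median risk ratio of 0.850 to 0.853 for SD 0.8 to 1.5. The logistic model converged in every run.

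**Step 5: what a shift is worth.** At N = 3,000, SE(log RR) = √[0.66/(0.34·1,500) + 0.60/(0.40·1,500)] = 0.048, so the 95% CI around 0.85 is about 0.77 to 0.93. A 2% move is log(1.02) / (1.96·0.048) = 0.21, or about a fifth of the half-width on the log scale.

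**The case against.** The best defence is that little hangs on this. The SAP calls it a sensitivity analysis and treats secondary analyses as exploratory. Both odds ratios will be shown, so a reader can see the gap and ask for the risk ratio, which limits hidden selection. When the trigger fires on non-collapsibility alone, the added risk ratio shows that nothing moved, which is useful. The firing rates rest on my cut-offs and assumed covariate strengths, and at a 10% cut-off they are at most about 6%. All of this stands and limits the weight of the point. It does not explain why the adjusted value on the primary scale should be conditional at all, when the planned model can supply it.

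Two stronger readings are tempting. One is that the log-link model cannot be fitted. The SAP names no distribution; the failure belongs to a log-binomial model with at least moderately prognostic covariates (SD of about 0.5 or more), and a log-link Poisson model fits. What can be said is that distribution and fallback are unspecified.

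The other is that the covariate list reveals data-driven choice. The SAP list is introduced as examples; it omits cardiopulmonary bypass and SOFA and adds baseline eGFR, SAPS II and surgical status. But the SAP says it was finalised before recruitment was complete and the database locked, and a SAP may refine a protocol's list. It later treats the model as settled, and entering a region main effect with the region interaction is ordinary practice. A missing reason and a loose abbreviation remain, which is tidying.

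**Conclusion.** The point holds as a cheap improvement to a supporting analysis. The adjusted risk ratio depends on an undefined, results-dependent trigger set on a non-collapsible scale, and an adjusted risk difference is not planned. Whether the trigger fires depends mainly on what counts as material: at SD 1.0 and RR 0.85, about 50% of trials at a 5% cut-off against about 6% at 10%.

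A reader might infer that the primary conclusion is at risk. The documents do not support that: the primary comparison is unadjusted, and its test, alpha and sample size do not involve this model. The expected numerical effect is small, since adjustment moved the risk ratio by more than 5% in at most about 1% of simulated trials.

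The algebraic point, that the odds ratios part while the risk ratio stays fixed, needs only a treatment effect and prognostic covariates. Its size, the firing rates and the log-binomial failure rates all rest on the assumed SDs, and the firing rates also on the cut-off.

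**What to change.** Before database lock, delete the conditional sentence and the log-link model it calls for. Replace them with wording such as: *From the adjusted logistic model, the covariate-standardised risk ratio and risk difference, obtained by averaging predicted risks over all analysed patients under each assignment, will always be reported with delta-method 95% CIs beside the adjusted odds ratio. Where imputation is used, they will be computed in each of the ten imputed datasets and pooled by Rubin's rules, the risk ratio on the log scale.* Keep the unadjusted comparison as primary and the site random-effect model as it stands.

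As secondary tidying, remove the abbreviation that leaves the covariate list open, and add one sentence saying how the list relates to the one in Protocol 2.10.

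The cost is SAP wording and modest programming, with no new data. The standardised estimates rely on the logistic model, and on imputation if baseline eGFR is often missing (Protocol 2.2.3 expects many patients without a pre-hospital creatinine). The adjusted odds ratio already carries the same reliance.
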